11.6.5.2 Guidelines for Treatment with Antibiotics

If there is evidence of respiratory infection that warrants treatment with antibiotics in the opinion of the Investigator or treating physician, the following guidelines should be used:

- The duration of treatment with antibiotics should be 7 to 14 days (dose and type according to local practice). If first antibiotic treatment fails and additional antibiotics are warranted, the total duration of antibiotic treatment should not exceed 30 days. If the duration of treatment with antibiotics needs to be greater than 30 days, the Investigator or treating physician should discuss the patient with the Medical Monitor and Sponsor to determine if the patient should remain in the study.
- Any course of antibiotics started within 7 days of finishing a previous course will be considered as treatment for a single exacerbation.

Use of antibiotics for the treatment of upper or lower respiratory tract infections is not considered a COPD exacerbation unless the patient experiences worsening of signs and symptoms associated with exacerbations as given above.

11.6.6 Recording COPD Exacerbations

Exacerbation details will be recorded in the exacerbation form of the eCRF. COPD exacerbations will not be recorded as adverse events (AE), unless they meet the definition of a serious adverse event (SAE). Pneumonia details will be recorded in the Pneumonia form of the eCRF and will also be recorded as an AE or SAE. Pneumonia should be confirmed by chest-x-ray. Every effort should be made to obtain a chest x-ray within 48 hours suspected pneumonia.

11.6.7 Study Continuation or Withdrawal Due to COPD Exacerbation

- Patients who experience a single COPD exacerbation during the treatment period may remain in the study and should continue to take their blinded study medication if possible and record their symptoms and rescue albuterol/salbutamol usage in their eDiary.
- Patients who experience a second COPD exacerbation and/or a severe COPD exacerbation that requires in-patient hospitalization will be discontinued from study treatment (Section 7.0).

11.7 Appendix 7: Adverse Events: Definitions and Procedures for Recording, Evaluating, Follow-up and Reporting

Definition of AE

- An AE is any untoward medical occurrence in a patient or subject, temporally associated with the use of blinded study medication, whether or not considered related to the blinded study medication.
- NOTE: An AE can therefore be any unfavorable and unintended sign (including an abnormal laboratory finding), symptom, or disease (new or exacerbated) temporally associated with the use of blinded study medication.

Events Meeting the AE Definition

- Any abnormal laboratory test results (eg, hematology, clinical chemistry) or other safety assessments (eg, ECG, radiological scans, vital signs measurements), including those that worsen from baseline, considered clinically significant in the medical and scientific judgment of the Investigator (ie, not related to progression of underlying disease).
- Exacerbation of a chronic or intermittent pre-existing condition including either an increase in frequency and/or intensity of the condition.
- New conditions detected or diagnosed after blinded study medication administration even though it may have been present before the start of the study.
- Signs, symptoms, or the clinical sequelae of a suspected drug-drug interaction.
- Signs, symptoms, or the clinical sequelae of a suspected overdose of either blinded study medication or a concomitant medication. Overdose per se will not be reported as an AE/SAE unless it is an intentional overdose taken with possible suicidal/self-harming intent. Such overdoses should be reported regardless of sequelae.
- “Lack of efficacy” or “failure of expected pharmacological action” per se will not be reported as an AE or SAE. Such instances will be captured in the efficacy assessments. However, the signs, symptoms and/or clinical sequelae resulting from lack of efficacy will be reported as an AE or SAE if they fulfil the definition of an AE or SAE.

Events NOT Meeting the AE Definition

- Any clinically significant abnormal laboratory findings or other abnormal safety assessments which are associated with the underlying disease, unless judged by the Investigator to be more severe than expected for the patient's condition.
- The disease/disorder being studied or expected progression, signs, or symptoms of the disease/disorder being studied, unless more severe than expected for the patient's condition.
- Medical or surgical procedure (eg, endoscopy, appendectomy): the condition that leads to the procedure is the AE.
- Situations in which an untoward medical occurrence did not occur (social and/or convenience admission to a hospital).
- Anticipated day-to-day fluctuations of pre-existing disease(s) or condition(s) present or detected at the start of the study that do not worsen.

Definition of SAE

If an event is not an AE per definition above, then it cannot be an SAE even if serious conditions are met (eg, hospitalization for signs/symptoms of the disease under study, death due to progression of disease).

An SAE is defined as any untoward medical occurrence that, at any dose:

a) Results in death**b) Is life-threatening**

The term 'life-threatening' in the definition of "serious" refers to an event in which the patient was at risk of death at the time of the event. It does not refer to an event, which hypothetically might have caused death, if it were more severe.

c) Requires inpatient hospitalization or prolongation of existing hospitalization

In general, hospitalization signifies that the patient has been detained (usually involving at least an overnight stay) at the hospital or emergency ward for observation and/or treatment that would not have been appropriate in the physician's office or outpatient setting. Complications that occur during hospitalization are AEs. If a complication prolongs hospitalization or fulfills any other serious criteria, the event is serious. When in doubt as to whether "hospitalization" occurred or was necessary, the AE should be considered serious.

Hospitalization for elective treatment of a pre-existing condition that did not worsen from baseline is not considered an AE.

d) Results in persistent disability/incapacity

- The term disability means a substantial disruption of a person's ability to conduct normal life functions.
- This definition is not intended to include experiences of relatively minor medical significance such as uncomplicated headache, nausea, vomiting, diarrhea, influenza, and accidental trauma (eg, sprained ankle) which may interfere with or prevent everyday life functions but do not constitute a substantial disruption.

e) Is a congenital anomaly/birth defect**f) Other situations:**

Medical or scientific judgment should be exercised in deciding whether SAE reporting is appropriate in other situations such as important medical events that may not be immediately life-threatening or result in death or hospitalization but may jeopardize the patient or may require medical or surgical intervention to prevent one of the other outcomes listed in the above definition. These events should usually be considered serious.

Examples of such events include invasive or malignant cancers, intensive treatment in an emergency room or at home for allergic bronchospasm, blood dyscrasias or convulsions that do not result in hospitalization, or development of drug dependency or drug abuse.

Recording and Follow-up of AE and/or SAE**AE and SAE Recording**

- When an AE/SAE occurs, it is the responsibility of the Investigator to review all documentation (eg, hospital progress notes, laboratory reports, and diagnostics reports) related to the event.
- The Investigator will then record all relevant AE/SAE information in the eCRF. Each event must be recorded separately.
- It is **not** acceptable for the Investigator to send photocopies of the patient's medical records to Sponsor/Sponsor's designee in lieu of completion of the Verona Pharma /AE/SAE eCRF page.
- There may be instances when copies of medical records for certain cases are requested by groups such as the Sponsor/Sponsor's designee, Health Authority, or Ethics Committee. In this case, all patient identifiers, with the exception of the subject/patient number, will be redacted on the copies of the medical records before submission to records to the Sponsor/Sponsor's designee.
- The Investigator will attempt to establish a diagnosis of the event based on signs, symptoms, and/or other clinical information. Whenever possible, the diagnosis (not the individual signs/symptoms) will be documented as the AE/SAE.

Assessment of Intensity

The Investigator will make an assessment of intensity for each AE and SAE reported during the study and assign it to one of the following categories:

- Mild: An event that is easily tolerated by the patient, causing minimal discomfort and not interfering with everyday activities.
- Moderate: An event that causes sufficient discomfort and interferes with normal everyday activities.
- Severe: An event that prevents normal everyday activities. An AE that is assessed as severe should not be confused with a SAE. Severe is a category utilized for rating the intensity of an event; and both AEs and SAEs can be assessed as severe.

An event is defined as 'serious' when it meets at least one of the predefined outcomes as described in the definition of an SAE, NOT when it is rated as severe.

Assessment of Chronicity

- Single occasion: Single event with limited duration.
- Intermittent: Several episodes of an event, each of limited duration
- Persistent: Event which remained indefinitely.

Assessment of Causality

- The Investigator is obligated to assess the relationship between blinded study medication and each occurrence of each AE/SAE. The AE must be characterized as unrelated, unlikely to be related, possibly related, probably related, or unknown (unable to judge).
 - “Probably related” conveys that there are facts, evidence, and/or arguments to suggest a causal relationship, rather than a relationship cannot be ruled out.
 - “Possibly related” suggests that the association of the AE with the blinded study medication is unknown; however, the AE is not reasonably supported by other conditions.
 - “Unlikely to be related” suggests that only a remote connection exists between the blinded study medication and the AE. Other conditions, including chronic illness, progression or expression of the disease state or reaction to concomitant therapy, appear to explain the reported AE.
 - “Unrelated” is used if there is not a reasonable possibility that the blinded study medication caused the AE.
 - All efforts should be made to classify the AE according to the above categories. The category “unknown” (unable to judge) may be used only if the causality is not assessable (eg, because of insufficient evidence, conflicting evidence, conflicting data, or poor documentation).
- The Investigator will use clinical judgment to determine the relationship.

- Alternative causes, such as underlying disease(s), concomitant therapy, and other risk factors, as well as the temporal relationship of the event to blinded study medication administration will be considered and investigated.
- The Investigator will also consult the Investigator's Brochure (IB) in his/her assessment.
- For each AE/SAE, the Investigator must document in the medical notes that he/she has reviewed the AE/SAE and has provided an assessment of causality.
- There may be situations in which an SAE has occurred and the Investigator has minimal information to include in the initial report to the Sponsor/Sponsor's designee. However, it is very important that the Investigator always make an assessment of causality for every event before the initial transmission of the SAE data to the Sponsor/Sponsor's designee.
- The Investigator may change his/her opinion of causality in light of follow-up information and send a SAE follow-up report with the updated causality assessment.
- The causality assessment is one of the criteria used when determining regulatory reporting requirements.

Action and Outcome

- Action taken with blinded study medication (none, blinded study medication stopped, blinded study medication temporarily interrupted)
- Other actions (none, concomitant medication, study discontinuation, hospitalization, other)
- The outcome and date of outcome according to the following definitions:
 - Recovered or resolved (adverse event disappeared)
 - Recovered or resolving (patient is recovering)
 - Not recovered or not resolved (adverse event remains without signs of improvement)
 - Recovered or resolved with sequelae (adverse event has resulted in permanent disability or incapacity)
 - Fatal
 - Unknown (only applicable if patient has been lost to follow-up)
- Seriousness (yes or no)

Follow-up of AEs and SAEs

- The Investigator is obligated to perform or arrange for the conduct of supplemental measurements and/or evaluations as medically indicated or as requested by the Sponsor/Sponsor's designee to elucidate the nature and/or causality of the AE or SAE as fully as possible. This may include additional laboratory tests or investigations, histopathological examinations, or consultation with other health care professionals.
- If a patient dies during participation in the study or during a recognized follow-up period, the Investigator will provide the Sponsor/Sponsor's designee with a copy of any postmortem findings including histopathology.
- New or updated information will be recorded in the originally completed eCRF.

- The Investigator will submit any updated SAE data to the Sponsor/Sponsor's Designee within 24 hours of receipt of the information.

Reporting of SAEs

SAE Reporting to the Sponsor/Sponsor's designee via an Electronic Data Collection Tool

- The primary mechanism for reporting an SAE to the Sponsor/Sponsor's designee will be the electronic data collection tool.
- If the electronic system is unavailable, then the study center will use the paper SAE data collection tool (see next section).
- The study center will enter the SAE data into the electronic system as soon as it becomes available.
- After the study is completed at a given study center, the electronic data collection tool will be taken off-line to prevent the entry of new data or changes to existing data.
- If a study center receives a report of a new SAE from a patient or receives updated data on a previously reported SAE after the electronic data collection tool has been taken off-line, then the study center can report this information on a paper SAE form (see next section) or to the Medical Monitor/SAE coordinator by telephone.
- Contacts for SAE reporting can be found in Section 11.2 on the Medical Monitor Contact Information page.

SAE Reporting to Sponsor/ Sponsor's Designee via Paper CRF if eCRF is not available

- If the eCRF is not available, facsimile transmission of the SAE paper CRF may be used to transmit this information to the Medical Monitor or the SAE coordinator.
- In rare circumstances and in the absence of facsimile equipment, notification by telephone is acceptable with a copy of the SAE data collection tool sent by overnight mail or courier service.
- Initial notification via telephone does not replace the need for the Investigator to complete and sign the SAE CRF pages within the designated reporting time frames.
- Contacts for SAE reporting can be found in Section 11.2 on the Medical Monitor Contact Information page.

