8.7.7 Disease-related Events and/or Disease-related Outcomes Not Qualifying as AEs or SAEs

COPD exacerbations are an expected disease-related outcome. COPD exacerbations will not be collected as an AE unless they meet the definition of an SAE. COPD exacerbations should be captured on the COPD exacerbation eCRF (Section 11.6).

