11.6.3.2 Severe

A severe exacerbation is defined as worsening symptoms of COPD requiring in-patient hospitalization.

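### Protocol Section 11.7 conflicts with Sections 8.7.7 and 11.6.6 on whether a hospitalised or fatal COPD exacerbation is a serious adverse event

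*Protocol*

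**What the plan says.** Protocol Section 8.7.7 states that "COPD exacerbations are an expected disease-related outcome" and that "COPD exacerbations will not be collected as an AE unless they meet the definition of an SAE". Section 11.6.6 repeats the recording rule. Both sections send every exacerbation to a dedicated eCRF form.

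Protocol Section 11.7 (Appendix 7) gives the general definitions:

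- Among events meeting the AE definition: "Exacerbation of a chronic or intermittent pre-existing condition including either an increase in frequency and/or intensity of the condition".
- Among events not meeting it: "The disease/disorder being studied or expected progression, signs, or symptoms of the disease/disorder being studied, unless more severe than expected" for the patient's condition. No criterion for that comparison is given.
- At the head of the SAE definition: "If an event is not an AE per definition above, then it cannot be an SAE even if serious conditions are met". The examples in parentheses are "hospitalization for signs/symptoms of the disease under study, death due to progression of disease".
- Inpatient hospitalisation and death are both seriousness criteria.

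Protocol Section 11.6.3.2 states: "A severe exacerbation is defined as worsening symptoms of COPD requiring in-patient hospitalization".

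Protocol Section 8.7.1 requires SAEs to reach the sponsor within 24 hours. SAP Sections 17.1.2 to 17.1.4 take treatment-emergent AEs (TEAEs) leading to discontinuation, serious events and fatal events from the Adverse Events page of the eCRF. SAP Section 4.1 says there is no data monitoring committee.

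**The concern.** The two sections written specifically for exacerbations assume that some of them are SAEs. The general SAE definition offers, as an example of what cannot be an SAE, almost exactly the event that defines a severe exacerbation. An investigator with a patient hospitalised for COPD worsening can follow either text and believe the protocol has been followed.

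At stake are the completeness and consistency of three safety outputs (serious, fatal and discontinuation TEAEs) and of 24-hour reporting, across approximately 116 planned centres. Safety over 24 and 48 weeks is a stated objective.

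**Working it through.** No arithmetic applies to the conflict itself. The check follows one event, a COPD worsening that leads to inpatient admission, through the text.

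**Starting point, common to both readings.** By Section 11.6.3.2 the event is a severe exacerbation. Admission also meets seriousness criterion c of Section 11.7. Sections 8.7.7 and 11.6.6 then ask whether the SAE definition is met.

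**Reading A: it is an SAE.**
1. The AE definition in 11.7 covers disease that is new or exacerbated, and a bullet lists exacerbation of a chronic pre-existing condition. The event is an AE.
2. It is serious by hospitalisation, so it is an SAE.
3. Under 8.7.7 and 11.6.6 it goes on the AE page, and under 8.7.1 it is reported within 24 hours.

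**Reading B: it is not an SAE.**
1. Section 8.7.7 calls exacerbations an expected outcome of the disease. The exclusion bullet in 11.7 removes signs and symptoms of the disease under study unless more severe than expected. An investigator who judges the event to be as expected concludes that it is not an AE.
2. The sentence heading the SAE definition then bars SAE status even with hospitalisation or death, and its examples name these outcomes.
3. The event goes on the exacerbation form only. The 24-hour route is not triggered, and the exception in 8.7.7 and 11.6.6 has almost no content.

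**What each reading does to the outputs.**

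| Output | Source | Reading A | Reading B |
|---|---|---|---|
| 24-hour report | Protocol 8.7.1 | Sent | Not sent |
| Serious TEAEs | SAP 17.1.3, AE page | Counted | Absent |
| Fatal TEAEs, if the patient dies | SAP 17.1.4, AE page | Counted | Absent |
| TEAEs leading to discontinuation | SAP 17.1.2, AE page | Counted if so recorded | Absent |
| Severe exacerbation | SAP 16.3.1.1, exacerbation page | Counted | Counted |

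The discontinuation row matters because Section 11.6.7 has study treatment discontinued after a severe exacerbation.

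The last row has one gap. A moderate exacerbation needs at least three days of corticosteroid or antibiotic treatment, and a severe one needs admission. An exacerbation that is fatal before either occurs would be on the exacerbation form but outside the moderate/severe analysis. Under Reading B it would also be outside the fatal TEAE table.

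**Size.** The documents give no expected rate of severe or fatal exacerbations, so no count can be derived. As a scale only, each 1% of the planned 800 patients is 800 × 0.01 = 8 patients, and only those at sites following Reading B would be missed.

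**The case against.** The strongest reply is that the text can be read so that every clause has effect. Sections 8.7.7 and 11.6.6 are recording rules. They do not say that an exacerbation fails the AE definition, so keeping it off the AE page does not by itself trigger the bar in 11.7. The bullet on chronic conditions makes an exacerbation an AE, and the exclusion bullet has its own exception. Protocol Sections 8.1.3 and 8.7 also allow COPD conditions found at Screening to become AEs if they worsen and meet the AE definition. The specific rule, stated twice, should prevail over a generic definition that does not name COPD exacerbations.

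Much of this stands. A reader might infer that the rules form a closed circle, or that a severe exacerbation is always or never an SAE. The documents do not support that, because the two routes above lead out. But the reply shows that Reading A is the better one, not that Reading B is excluded. The exclusion bullet and the examples still stand, and the exception has no criterion.

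Three further inferences also go too far:

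- **Bias between arms.** Protocol Section 6.4 restricts treatment knowledge at sites, and no mechanism is shown by which classification would differ by arm. Under-counting in both arms is what the text supports.
- **Lost events.** Exacerbations have their own form, and Protocol Section 8.3.3.4 records all-cause hospitalisations. What may be missing is the SAE classification and report.
- **Severe exacerbation as the most common serious event.** No figure in the documents supports this.

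The absence of a monitoring committee adds little, since nothing shows that such a committee would check how sites classify events.

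**Conclusion.** The inconsistency is real and lies in the current text. Sections 8.7.7 and 11.6.6, and the chronic-condition bullet in 11.7, lead to SAE status for a hospitalised exacerbation. The exclusion bullet, the sentence heading the SAE definition and its examples lead away from it. If sites follow different passages, 24-hour reports and the serious, fatal and discontinuation TEAE tables will be inconsistent or incomplete for these events.

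The effect is limited to safety reporting. Moderate/severe exacerbation counts are largely unaffected. The conclusion assumes that sites work from the protocol text. Separate guidance or safety-data reconciliation outside these two documents could reduce the problem, but the documents describe neither for this purpose. The correction should be made, because it is cheap and concerns serious events.

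**What to change.** Reconcile Sections 8.7.7, 11.6.6 and 11.7:

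1. State in 11.7 that COPD exacerbations meeting a seriousness criterion are handled under 8.7.7 and 11.6.6. The statement is needed in two places, the disease-under-study exclusion bullet and the sentence heading the SAE definition. Changing only the second would leave the source of the ambiguity in place.
2. Keep the examples in parentheses, but limit them to disease progression other than exacerbations.
3. Before database lock, check every severe or fatal event on the exacerbation form against the AE page, and query those without a matching SAE record.

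This aligns the general definition with the protocol's own rule for exacerbations. It concerns recording, not patient management.

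The cost is a short amendment with ethics committee and, where applicable, regulatory approval (Protocol Section 11.2), a site reminder, one reconciliation listing and possibly more SAE reports.
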